Statistical Analysis Plan for Social Anxiety MDMA-Assisted Therapy Investigation (SAMATI)

ID: IUSA5

Clinicaltrials.gov identifier: NCT05138068

Document date: August 8, 2022

Statistical Analysis Plan

Contents

SAMATI Statistical Analysis Plan	1
Study Design	2
Randomization Plan	2
Primary Outcome Measures	3
Leibowitz Social Anxiety Scale (LSAS)	3
Secondary Outcome Measures	3
Sheehan Disability Scale (SDS)	3
Internalized Shame Scale (ISS)	3
Acceptance of Shame and Embarrassment Scale (ASES)	3
Interpersonal Needs Questionnaire – Thwarted Belongingness Subscale (INQ)	3
Hidden Self Scale (HSS)	3
Self-Compassion Scale – Short Form (SCS)	4
Analytic plan	4
Primary Analyses	4
Secondary Analyses	4
Other Pre-registered Data Analyses	5

Study Design

This is a randomized, open-label delayed treatment study to assess the safety and effect of MDMAassisted therapy in treating 20 participants diagnosed with moderate-to-severe social anxiety disorder (SAD) of the generalized subtype. Half of the enrolled participants (N = 10) will proceed immediately into treatment once enrolled (immediate treatment group), and half (N = 10) will receive the experimental treatment after an initial 16 week wait (Delayed treatment group).

The primary outcome assessment will occur at two weeks post final integration session. There will also be a 6-month follow up assessment (28 weeks after final integration session). The study is preregistered at clinicaltrials.gov.

Randomization Plan

We will use permuted block randomization with random blocks of 2 and 4 to minimize the possibility of guessing. This randomization will be conducted by a PhD level scientist who is not involved in the trial so the study team can remain blinded.

Primary Outcome Measures

Leibowitz Social Anxiety Scale (LSAS)

The primary outcome assessed in the study is social anxiety symptom severity measured LSAS (Heimberg et al., 1999). The LSAS is a 24-item, semi-structured interview on the severity of social anxiety disorder, which assesses fear (0 to 3 = none, mild, moderate, severe) and avoidance (0 to 3 = never, occasionally, often, usually) of 24 social situations over the previous week, providing an overall social anxiety severity rating and subscale scores for performance fear, performance avoidance, social fear, and social avoidance. Scores range from a minimum of 0 to maximum of 144 with higher scores indicating a worse outcome.

Secondary Outcome Measures

Sheehan Disability Scale (SDS)

The SDS is a clinician-rated assessment of functional impairment (Sheehan, 1986). The items indicate degree of impairment in the domains of work/school, social life, and home life, with response options based on an eleven-point scale (0=not at all to 10=extremely), and five verbal tags (not at all, mildly, moderately, markedly, extremely) and has been validated for use in clinical trials (K. H. Sheehan & Sheehan, 2008) and psychiatric impairment (Leon, Olfson, Portera, Farber, & Sheehan, 1997). The SDS takes 1 to 2 minutes to complete.

Internalized Shame Scale (ISS)

The ISS is a 24-item self-report questionnaire measuring internalized shame that has been used in numerous studies of trait shame and has been demonstrated to have good construct validity and reliability in both clinical and nonclinical populations (del Rosario & White, 2006). This measure is included to assess changes in shame, which is thought to be important to SAD, and in relation to MDMA, which has been hypothesized to facilitate self-acceptance.

Acceptance of Shame and Embarrassment Scale (ASES)

The ASES is a 17 item self-report measure (Sedighimornani, Rimes, Verplanken, & Gauntlett-Gilbert, 2019) intended to assess avoidance of shame and embarrassment, two emotions hypothesized to be central to the experience of SAD. The measure shows good internal reliability, factor structure, and correlation with theoretically meaningful constructs (Sedighimornani et al., 2019). This measure is being included because MDMA has been theorized to reduce avoidance.

Interpersonal Needs Questionnaire – Thwarted Belongingness Subscale (INQ) The 9-item Thwarted Belongingness subscale from the INQ (Freedenthal, Lamis, Osman, Kahlo, & Gutierrez, 2011) will be used to assess the degree to which participants feel a sense of belonging, connection, and closeness with others. A recent comprehensive review of measures of social connectedness concluded the INQ was the most psychometrically sound measure (Hare Duke, Dening, de Oliveira, Milner, & Slade, 2019).

Hidden Self Scale (HSS)

The HSS (Levinson, Rodebaugh, Lim, & Fernandez, 2015) is a 4-item subscale of the Core Extrusion Schema–Revised and is thought to measure attempts to hide ones "true self" from others so as to avoid potential ostracism and rejection. This measure was created for use in SAD populations. The measure has demonstrated good psychometrics and the HSS subscale predicts the intensity of social interaction anxiety. This measure is included based on the idea that MDMA may increase participants' sense of authenticity and reduce fear of revealing vulnerable parts of oneself.

Self-Compassion Scale – Short Form (SCS)

The SCS short form (Raes, Pommier, Neff, & Van Gucht, 2010) is a 12-item self-report measure of selfcompassion, or responding to one's own failure, suffering or inadequacies with kindness and compassion and recognizing one's own flaws and suffering as part of common human experience. Because the measure is being administered repeatedly and we wanted it to be sensitive to change, we modified the measure slightly from to refer only to experiences in the last week. It is estimated to take about 3 minutes to complete. This brief measure has been shown to correlate highly with the well-validated longer version of this scale and to have excellent psychometric characteristics itself (Raes et al., 2010).

Analytic plan

Primary Analyses

Primary outcome analyses are intent-to-treat comparing mean scores on the LSAS at primary outcome assessment in the immediate treatment condition (n = 10) compared to the 16-week re-assessment in the delayed treatment condition (n = 10). A participant is considered eligible for the ITT analysis if they have completed at least one Experimental Session and at least one LSAS assessment beyond baseline. We will use an independent samples t-test to compare means across groups. Hedges' G will be reported as measure of effect size with confidence intervals calculated at 95%.

Secondary Analyses

Descriptive statistics for all primary and secondary outcome variables will be calculated.

To examine the change in social anxiety severity for all participants who received MDMA-assisted therapy, we will also collapse participants in the immediate and delayed treatment groups (N = 20) and use a paired samples t-test to compare mean change in LSAS scores from baseline to primary outcome.

To examine sustained treatment effects over time for the entire sample (N=20), we use a paired sample ttest to compare LSAS mean scores at baseline with LSAS mean scores at 6-month follow up. Hedges' G will be used to estimate the effect size and confidence intervals will be calculated at 95%. If there is significant heterogeneity in variance across time points, Glass' Delta will be used to estimate the effect.

Secondary outcome analyses are intent-to-treat comparing mean scores on the measure (SDS, ASES, ISS, INQ, SCS, and HSS) at primary outcome assessment in the immediate treatment condition (n = 10) compared to the 16-week re-assessment in the delayed treatment condition (n = 10). We will use an independent samples t-test to compare means across groups. Hedges' G will be reported as measure of effect size with confidence interval calculated at 95%.

Change in secondary measures will be analyzed using the full sample by collapsing immediate and delayed treatment groups (N = 20) and conducting a series of paired samples t-tests comparing all secondary outcome measures (SDS, ASES, ISS, INQ, SCS, and HSS) at baseline, primary outcome and 6 month follow up.

We will report correlations between the primary outcome measure (LSAS) and secondary outcome measures. We will estimate the strength of the relation between change in social anxiety symptom

severity as measured by the LSAS and change in secondary outcome measures from baseline assessment to post-treatment. Specifically, we will subtract baseline scores from primary outcome scores for each measure and calculate bivariate correlations between this change score for the LSAS and change in each secondary outcome measure.

Other Pre-registered Data Analyses

Additional exploratory analyses not described here will be outlined in subsequent pre-registrations and posted to publicly available online repositories prior to data analysis.

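### The intent-to-treat set admits participants who stop early, but the immediate-arm score it tests depends on finishing treatment, so the primary t-test can become a completer analysis

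*SAP*

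**What the plan says.** Under Study Design, the SAP sets the time of the main outcome: "The primary outcome assessment will occur at two weeks post final integration session". The same section has the delayed group wait 16 weeks before treatment, while the immediate group starts treatment once enrolled.

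Under Analytic plan, Primary Analyses, the comparison is labelled intent-to-treat. It sets mean LSAS "at primary outcome assessment in the immediate treatment condition (n = 10) compared to the 16-week re-assessment in the delayed treatment condition". An independent samples t-test is used. A participant enters the set after having "completed at least one Experimental Session and at least one LSAS assessment beyond baseline".

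Under Secondary Analyses, the same contrast and test are specified for the SDS, ASES, ISS, INQ, SCS and HSS.

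The SAP does not say which score represents someone who meets the inclusion rule but has no score at the analysed time point.

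**The concern.** The inclusion rule and the analysed time point do not fit together. The rule lets in people who stop early, because "at least one LSAS assessment beyond baseline" is enough on the outcome side. The outcome, however, is a single assessment whose date depends on the end of treatment. A t-test on that assessment uses only those who have it.

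If early stoppers drop out of the immediate arm, the comparison is between completers and controls under an intent-to-treat label. If they are instead scored soon after they stop, they are measured at a different time since enrolment from the controls. That matters because the LSAS asks about the previous week, so each score belongs to the week in which it is taken.

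With 10 per arm in an open-label trial, one participant is 10% of an arm. The choice should not be left until outcomes are known.

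**Working it through.** The SAP gives no effect size, standard deviation, dropout rate or power, so there is no figure of its own to reproduce. The check has four steps.

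**1. When do the arms coincide?** Inputs: 2 weeks after the last integration session (Study Design) and week 16 (Primary Analyses).

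Immediate-arm assessment week = week of last integration session + 2. Setting this equal to 16 gives 16 − 2 = week 14. The arms are aligned for anyone whose last integration session falls at week 14. If it fell at week 8, the assessment would be at week 10, which is 6 weeks before the controls. If it fell at week 18, the assessment would be at week 20, which is 4 weeks after them. Weeks 8 and 18 are assumed examples.

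**2. What happens to an immediate-arm participant who stops after one Experimental Session and has one later LSAS?** The inclusion rule admits this person. The outcome then has two readings:

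| Meaning of the last integration session | Consequence |
|---|---|
| Last one attended | Scored before week 16, earlier than the controls |
| Last one scheduled | No value at the analysed time point, so dropped by the t-test despite being in the set |

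The text supports either reading. Under the second, the stated n = 10 in the immediate arm is not met.

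**3. How large could the effect of dropping be?** Assumptions, none of them from the SAP: the k participants dropped from the immediate arm have no benefit, the other 10 − k have mean effect d, and the delayed arm is complete.

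Effect in all 10 = d × (10 − k)/10. Overstatement factor = d ÷ [d × (10 − k)/10] = 10/(10 − k).

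| Dropped (k) | Effect in all 10 | Overstatement factor |
|---|---|---|
| 1 | 0.9d | 10/9 = 1.11 |
| 2 | 0.8d | 10/8 = 1.25 |
| 3 | 0.7d | 10/7 = 1.43 |

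If stoppers had some benefit, the factors would be smaller. If they left because they had improved, the direction would reverse.

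**4. Can the delayed arm also lose participants?** Yes. The Experimental Session requirement is not limited to one arm. Delayed-arm participants reach their first session only after the 16-week wait. Read literally, someone who gives a week-16 LSAS and then leaves before treatment is excluded because of something that happened after the outcome was measured. In either arm, a participant who leaves before any session is also excluded.

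**The case against.** The strongest reply is that the 16-week wait was evidently chosen to match the length of treatment, and that visit windows, the session schedule and any early-termination visit belong in the protocol, which is not at hand. This stands as far as timing goes: the lack of a window in the SAP is not an error in itself, and on-schedule completers are probably compared at the same time. It does not answer step 2. Which score enters the primary test for someone whom the SAP itself declares eligible is an analysis rule, and the two rules the SAP states do not agree for early stoppers.

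A second reply is that measuring after a completed course is a reasonable target for a small open-label study, and that week 16 would catch late finishers in mid-treatment. That is a fair trade-off, and a reason to keep the treatment-anchored score as a sensitivity analysis. It is not what an intent-to-treat label promises.

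A reader might infer more than the document supports in two ways:

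- **That participants can be lost from the treated side only, so the bias must favour treatment.** Step 4 shows that delayed-arm participants with a week-16 score can also be excluded. The net direction depends on who leaves and why.
- **That the timing mismatch itself shifts the LSAS difference by a calculable amount.** The SAP gives no rate of natural change and no distribution of overruns, and early and late assessments would partly offset each other. If 2 of 10 overran by 4 weeks, the arm's mean time would move by only 2 × 4/10 = 0.8 weeks.

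**Conclusion.** The point holds in a limited form. As written, the intent-to-treat set and the analysed time point are inconsistent for immediate-arm participants who stop early, and the t-test can become a completer analysis. The same applies to all six secondary between-arm comparisons. Separately, the Experimental Session requirement makes the set narrower than all randomised participants in both arms.

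The size and direction of any bias cannot be derived from the SAP. The factors of 1.11 to 1.43 illustrate one case only: 1 to 3 of 10 dropped from the immediate arm, no benefit in those dropped, and nobody lost from the delayed arm. If everyone finishes on schedule, the timing problem does not arise. An early-termination visit in the protocol could reduce the loss of scores, but the SAP would still have to say which score is analysed. The matter should be settled before analysis because the remedy is cheap.

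**What to change.** For the primary and the six secondary between-arm comparisons:

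- Define the outcome in both arms as the score at 16 weeks from enrolment, within one stated window.
- Collect and analyse it for all randomised participants, whether or not treatment was completed.
- Remove the Experimental Session requirement from the intent-to-treat set.
- Use the visit two weeks after the last integration session as the week-16 value when it falls inside the window.
- For late finishers, report the treatment-anchored score as a sensitivity analysis.
- State in advance how a missing week-16 score is handled, since someone who declines further ratings is missing on either clock.

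Keep the treatment-anchored visit for the pooled pre-post analyses, where it fits the question.

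The cost is a change of SAP wording, an extra rating for the few immediate-arm participants whose schedule does not meet week 16 (which may also need a matching change to the visit schedule), and a possibly less favourable estimate, because late finishers may be scored before their treatment ends.

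### The intent-to-treat set requires an Experimental Session, which no delayed-arm participant has had at the 16-week comparison, so the control arm is either empty or selected on a later event

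*SAP*

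**What the plan says.** Study Design sets the timing of treatment in the control arm: "half (N = 10) will receive the experimental treatment after an initial 16 week wait (Delayed treatment group". It also fixes when the immediate arm is measured: "The primary outcome assessment will occur at two weeks post final integration session".

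Analytic plan, Primary Analyses, gives the label and the immediate-arm side of the comparison: "Primary outcome analyses are intent-to-treat comparing mean scores on the LSAS at primary outcome assessment in the immediate treatment condition (n = 10". The control side is given in the remainder of that sentence: "compared to the 16-week re-assessment in the delayed treatment condition (n = 10". The next sentence defines who enters. A participant is "eligible for the ITT analysis if they have completed at least one Experimental Session and at least one LSAS assessment beyond baseline". The rule has no arm-specific version and no date at which it is applied. The test follows: "We will use an independent samples t-test to compare means across groups", with Hedges' g and a 95% confidence interval.

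Secondary Analyses uses the same label for the six between-arm comparisons (SDS, ASES, ISS, INQ, SCS, HSS): "Secondary outcome analyses are intent-to-treat comparing mean scores on the measure". The time points and the 10 against 10 are the same. No other definition of the set is given, so the natural reading carries the rule over.

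**The concern.** The control value in the primary test is measured before that arm receives any treatment. A rule that demands treatment cannot be met by that arm at that moment. If it is applied later instead, a delayed participant's week-16 score counts only if the participant goes on to start treatment. Someone who is assessed at week 16 and then withdraws, declines or no longer needs treatment is removed because of an event that follows the outcome and may be caused by it.

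In the immediate arm the same words act differently. They remove people who leave soon after randomisation, before a first session. The two arms are thus filtered at different times and by different mechanisms, and the two selections cannot be assumed to cancel.

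At stake is the protection that randomisation gives to the primary comparison and, by the natural reading, to the six secondary ones. The trial is open-label and has 10 per arm, so one or two exclusions can move the result. An ambiguous rule also lets the control set be settled after the data are seen.

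**Working it through.** **1. The plan's own figure.** The SAP states n = 10 for the delayed arm. Apply the eligibility rule to the timeline, with k the number of delayed participants who have a week-16 score but never start treatment:

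| When the rule is applied | Sessions completed by the delayed arm | Delayed n | Result |
|---|---|---|---|
| At the week-16 comparison | 0 | 0 | 10 vs 0; t-test and Hedges' g undefined |
| At study end | at least 1 only for those who later start | 10 − k | an observed score is dropped for each of the k |
| Condition removed | not required | 10 | matches the SAP |

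The stated 10 cannot be reached under the first reading. Under the second it is reached only if k = 0.

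**2. Size under the second reading.** Assumptions that are not in the SAP: k from 1 to 3; normally distributed scores; no true effect; two-sided alpha 0.05, inferred from the 95% intervals; LSAS SD of 20 points (range 15 to 25).

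Let ρ be the correlation between the week-16 score and the tendency to leave, with lower (better) scorers leaving. The expected three lowest of 10 standard normal values are −1.539, −1.001 and −0.656. The remaining control mean shifts upward by

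shift = ρ × (sum of the k lowest, sign reversed) / (10 − k).

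For ρ = 1:
- k = 1: 1.539 / 9 = 0.17 SD
- k = 2: (1.539 + 1.001) / 8 = 0.32 SD
- k = 3: (1.539 + 1.001 + 0.656) / 7 = 0.46 SD

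For ρ = 0.5 the shifts are half as large: about 0.09, 0.16 and 0.23 SD.

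Simulating 100,000 null trials of 10 vs 10 − k gives these two-sided type I error rates (nominal 5%):

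| k | ρ = 0.5 | ρ = 1 |
|---|---|---|
| 1 | about 5.5% | about 7.5% |
| 2 | about 6.4% | about 11.7% |
| 3 | about 7.5% | about 17.0% |

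The extra errors fall on one side. For k = 2, the chance of a significant result in favour of treatment is about 5.2% (ρ = 0.5) or 11% (ρ = 1), against 2.5% nominal.

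In LSAS points for k = 2:
- ρ = 0.5: 0.16 × 20 = 3.2 (0.16 × 15 = 2.4 to 0.16 × 25 = 4.0)
- ρ = 1: 0.32 × 20 = 6.4 (0.32 × 15 = 4.8 to 0.32 × 25 = 8.0)

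**3. Limits of the illustration.** With k = 0, or with leaving unrelated to score (ρ = 0), there is no bias and the error rate stays at 5%. If the most severe participants leave, the shift has the same size and the opposite sign.

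**4. Precision.** Assuming 80% power, the minimum detectable difference is 1.33 SD for 10 vs 10, and 1.37, 1.42 and 1.48 SD for delayed n of 9, 8 and 7. The loss of precision is small beside the possible bias.

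**The case against.** The best reply is that nobody intends an empty control arm. The sentence before the rule says 10 against 10, the secondary comparisons repeat it, and no cut-off date says eligibility is judged at week 16. The session condition was probably meant for treated participants. On the study-end reading, the plan expects all 10 delayed participants to be treated and pools N = 20, so k may well be 0 and the bias nil. The SD, the number of leavers and the correlation all come from outside the SAP. The sign is unknown. On a two-sided basis the moderate case raises the error only from 5% to about 6.4%. The Secondary Analyses text also does not repeat the rule.

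Much of this stands as a limit on size. The empty arm shows that the wording cannot be carried out; it is not a forecast. The bias is conditional, and its reach into the secondary outcomes is an inference, though the natural one.

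It does not rescue the rule. The sentence sits under Primary Analyses and defines the intent-to-treat set for both arms. The reading that avoids an empty arm still drops measured outcomes because of later events. Nor is this an ordinary modified intent-to-treat set: such a set needs a criterion that both arms can meet before the outcome, and here one arm cannot. If something else was meant, the sentence has to say so.

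**Conclusion.** The concern holds, and the rule must be corrected before analysis. Three statements in the SAP cannot stand together: treatment of the delayed arm only after 16 weeks, a week-16 control value from 10 participants, and entry only after a session. This contradiction needs no assumption. The size of any bias does. For two leavers and no true effect it is about 0.16 SD under moderate dependence on score and 0.32 SD in the worst case, on the assumptions set out above. The document does not allow the actual size or direction to be known.

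**What to change.** Replace the eligibility sentence under Primary Analyses. Define the set for the primary and the six secondary between-arm comparisons as all randomised participants, analysed in the arm assigned, whether or not they ever have an Experimental Session. Every observed week-16 score in the delayed arm then counts.

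Add how a missing score at the comparison is handled. Without that, a t-test on observed values would still lose an immediate-arm participant who leaves before the first session and has no LSAS at the primary outcome assessment.

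Keep the one-session condition only for the pooled pre-post analyses of treated participants, and state it there.

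The cost is one sentence for the set and another for missing scores, with no new participants and no new assessments. The estimate may be slightly less favourable to treatment. The change restores the 10 against 10 that the SAP already states.

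### The LSAS and six secondary between-arm comparisons ignore each measure's collected baseline: a valid test, but probably inefficient with 10 per arm

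*SAP*

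**What the plan says.** Under Primary Analyses, the SAP describes the main analysis as "comparing mean scores on the LSAS at primary outcome assessment in the immediate treatment condition (n = 10) compared to the 16-week re-assessment" in the delayed arm, followed by "We will use an independent samples t-test to compare means across groups". The variable is therefore the post score, not a change score, and there is no covariate.

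Under Secondary Analyses, the same design is repeated for SDS, ASES, ISS, INQ, SCS and HSS: "Secondary outcome analyses are intent-to-treat comparing mean scores on the measure", with the same test.

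Baselines are used, but only in analyses that do not compare the arms. With the arms pooled, the SAP will "use a paired samples t-test to compare mean change in LSAS scores from baseline to primary outcome" and run paired tests on all six secondary measures that include baseline. For the correlations it states "we will subtract baseline scores from primary outcome scores for each measure and calculate bivariate correlations". Calling the delayed arm's 16-week score a re-assessment also implies an earlier, pre-wait score in that arm.

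The Randomization Plan describes permuted blocks of 2 and 4 and mentions no stratification by baseline severity.

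**The concern.** The seven between-arm tests are the only analyses protected by randomisation, and they are the only LSAS and secondary-outcome tests that make no use of baseline. Where a participant's post score depends partly on how severe they were at entry, that variation stays in the error term. With 20 participants it is a large part of what limits the result.

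This is a question of precision, not of bias. Given a chance baseline difference D (in SD, with equal SDs at the two times), the unadjusted estimate is shifted by r × D. Over repeated randomisations these shifts average to zero, and their spread is already inside the t-test's standard error. They are not a second error to be added to it.

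What is at stake is the width of the interval around the treatment difference and the chance of detecting a real one. Adjustment that is left until the data have been seen also becomes a discretionary choice.

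**Working it through.** **Inputs from the SAP.** n = 10 per arm; independent samples t-test on post scores; 95% confidence level.

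**Assumptions.** The SAP gives no effect size, SD, test alpha or baseline-outcome correlation, so there is no stated figure to reproduce. I take a two-sided 0.05 level, no dropout, standardised effects d around 1.0 to 1.5, and r from 0 to 0.7.

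**Planned t-test.**
- SE = sqrt(2/10) = 0.447 SD, with df = 18.
- Mean 95% CI width = 2 × 2.101 × 0.986 × 0.447 = 1.85 SD. Here 2.101 is the t quantile and 0.986 is the expected ratio of sample to true SD on 18 df.
- Power (noncentral t): 56.2% at d = 1.0 and 88.7% at d = 1.5. Power reaches 80% at d = 1.32.

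**ANCOVA with baseline as covariate.**
- SE = sqrt(0.2 × (1 − r²) × 17/16) SD, with df = 17. The factor 17/16 = 1 + 1/16 is the average cost of chance baseline imbalance with N = 20.
- Example at r = 0.5: sqrt(0.2 × 0.75 × 1.0625) = 0.399 SD.
- Power is the noncentral t averaged over the baseline difference and the within-arm baseline sum of squares.

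| r | SE (SD) | Mean CI width (SD) | Power at d = 1.0 | d for 80% power |
|---|---|---|---|---|
| t-test, any r | 0.447 | 1.85 | 56.2% | 1.32 |
| 0 | 0.461 | 1.92 | 53.7% | 1.37 |
| 0.2 | 0.452 | 1.88 | 55.3% | 1.34 |
| 0.3 | 0.440 | 1.83 | 57.5% | 1.31 |
| 0.5 | 0.399 | 1.66 | 65.8% | 1.19 |
| 0.6 | 0.369 | 1.53 | 72.6% | 1.10 |
| 0.7 | 0.329 | 1.37 | 81.7% | 0.98 |

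The last six rows are ANCOVA. A simulation of 100,000 trials per setting agrees with these powers to within 0.2 points and gives type I error of 0.049 to 0.050. At d = 1.5 power is 88.7% unadjusted against 94.2% at r = 0.5.

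**Break-even.** The SEs are equal when (1 − r²) × 17/16 = 1, so r = sqrt(1/17) = 0.243. On mean CI width, with the lost degree of freedom, break-even is about 0.25. On power it is 0.244 to 0.257 for d = 0.8 to 1.5.

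**Equivalent sample size.** 10 / (0.75 × 1.0625) = 12.5 per arm at r = 0.5; 10 / (0.51 × 1.0625) = 18.5 per arm at r = 0.7.

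**Worst case.** At r = 0, over d = 0.4 to 2.0, the largest power loss is 2.7 points, at d = 1.2.

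**Different r in the two arms** (delayed/immediate; equal variances, d = 1.0, simulated; t-test 56%): 66% at 0.7/0.3, 63% at 0.7/0.2, 59% at 0.6/0.1, 56% at 0.5/0 and 55% at 0.3/0. Type I error is 0.049 to 0.053.

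**Chance imbalance, for illustration only.** The baseline difference has SD sqrt(2/10) = 0.447, so it exceeds 0.5 SD in either direction with probability 26%. At r = 0.6 a 0.5 SD difference moves the unadjusted estimate by 0.6 × 0.5 = 0.3 SD. The standard errors above already contain this.

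**The case against.** The strongest reply is that nothing here is wrong. The SAP names the variable, time points, test and effect measure consistently, and the test holds its size. Whether adjustment helps depends wholly on r, which the SAP does not give. The one relevant fact in the document, that the sample is "20 participants diagnosed with moderate-to-severe social anxiety disorder (SAD) of the generalized subtype", restricts the baseline range and points towards a lower r. A common high r is also the favourable case: one arm is treated while the other waits, and variable response could weaken the correlation in the treated arm. If the treated arm's SD is also 1.5 times the other's (assumed; d = 1.25 in control-arm SDs), simulated power for the t-test against ANCOVA is 55% v 62% at 0.7/0.3, 55% v 60% at 0.7/0.2, 54% v 56% at 0.6/0.1 and 55% v 54% at 0.5/0, with ANCOVA type I error of 5.3 to 5.5%.

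Much of this stands. The gain is not certain, it is negligible near r = 0.3, and the 73% and 82% powers need r of 0.6 to 0.7 in both arms. The word probably rests on a judgement that two scores on one instrument in the same person will usually correlate above 0.25, not on a figure in the SAP.

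It does not defeat the point, because the stakes are lopsided: under 3 power points lost at worst, against about 10 gained at r = 0.5 and 25 at r = 0.7 (d = 1.0). Nor does the SAP cover this elsewhere; the later pre-registrations it foresees are for exploratory analyses.

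Two limits also stand. Valid refers to the choice of test only: the rule that ties ITT eligibility to having had an Experimental Session is a separate matter, which adjustment does not cure. And the usual interval for Hedges' g does not carry over unchanged to an adjusted difference.

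**Conclusion.** The concern holds. All seven between-arm comparisons leave out a baseline that the SAP uses for the same measures elsewhere. The planned t-test is a valid choice but probably an inefficient one. If r is 0.5 in both arms, adjustment cuts the variance by 20% and the mean CI width from 1.85 to 1.66 SD. If r is 0.7, it cuts the variance by 46% and the width to 1.37 SD. Below r of about 0.24 to 0.25 it loses slightly.

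These sizes assume 10 analysed per arm, a two-sided 0.05 level, no dropout and approximately normal scores. The table also assumes equal variances and one r for both arms. This is a recommended improvement, held with medium confidence because r is unknown for the LSAS and for each secondary measure.

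**What to change.** - **Primary analysis:** prespecify an ANCOVA of LSAS on arm with baseline LSAS as covariate. The outcome stays as planned: the primary outcome assessment in the immediate arm and the 16-week re-assessment in the delayed arm. Report the adjusted mean difference in LSAS points with its 95% CI.
- **Covariate in the delayed arm:** state that it is the baseline before the 16-week wait, because the 16-week score is the outcome.
- **Secondary measures:** use the same model for each of the six, with that measure's own baseline, and note that r is unknown for each.
- **Effect size:** compute Hedges' g as the adjusted difference over the unadjusted pooled SD, with the small-sample correction, and name the method for its interval.
- **Sensitivity analysis:** keep the planned t-test, with its g and usual interval.

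The cost is SAP wording and one degree of freedom (18 to 17), settled before any outcome data are examined. No new data are needed, and the power loss is under 3 points if r is near zero.
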